## 1. BACKGROUND

Transposition of the great arteries, the most common cyanotic congenital heart lesion found in neonates, accounts for 5%–7% of congenital cardiac malformations.

Arterial switch surgery is now the treatment of choice for transposition of the great arteries. In this procedure, the aorta and main pulmonary artery are transected, switched, and re-anastomosed to the correct ventricle. The coronary arteries and a small portion of aortic sinus are excised when the aorta is transected and are re-implanted once the aorta is connected to the left ventricular outflow tract.

Most complications and mortality occur within the first year of life, and are secondary to myocardial ischemia or infarction associated with relocation of the coronary arteries at surgery. Nonetheless, follow-up studies have revealed a significant prevalence (7-8%) of coronary stenosis, occlusions and late death in an otherwise symptom-free patient population.

Other pathologic condition affecting coronary arteries during pediatric age, with a lower incidence than transposition of coronary arteries, are: Kawasaki disease, primary dilatative cardiomyopathy of undetermined nature, ALCAPA syndrome and other coronary artery anomalies of origin and pathway, coronary fistula, coronary atresia, familial hypercholesterolemia, bicuspid aortic valve, chest pain or dispnea related to exercise of suspected coronary nature.

Following current practice, pediatric patients affected by or with suspected coronary artery disease undergo to Exercise Test, Eco stress and Coronary Angiography. While coronary angiography (CA) is considered the gold standard for detection of coronary lesions necessitating possible interventions, CA is a invasive and x-ray exposing technique which cannot be included in regular follow-up in asymptomatic children.

Cardiovascular Magnetic Resonance imaging (cMRI) provides both morphologic and functional information that can be decisive in the treatment of neonates and infants with congenital heart disease. Thanks to its non-invasiveness and lack of ionizing radiation, cMRI is now becoming a major imaging tool in pediatric congenital heart disease.

## 2. OBJECTIVES

### **Primary Objective:**

- To verify the concordance between stress cMRI and conventional technique (angiography, eco-stress) in evaluation of pediatric patient with suspected coronary artery disease.

### **Secondary Objectives:**

- To optimize the scan protocol and the sequence parameters
- To investigate the clinical compliance of stress induced cardiac MRI in pediatric patients
- To test the ability of stress cMRI to visualize coronary arteries morphological irregularities, the corresponding wall motion abnormalities and perfusion - viability features
- To find a correlation between cMRI data and clinical status and other diagnostic tools, parameters and variables.
- To demonstrate the advantage of stress cMRI over cMRI in evaluation of pediatric patient with

suspected coronary artery disease.

**Primary Endpoint:**

- Agreement of results between stress cMRI and the current practice constituted by Exercise test, Stress Cardiac Ultrasound and Invasive Angiography.

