#### 4.4 STATISTICAL CONSIDERATIONS

Data will be described as means, standard deviation (SD) and medians with a range for continuous variables, while absolute and relative frequencies will be used for categorical variables.

Categorical data will be compared by chi-square test or by Fisher's exact test in case of expected frequencies  $<5$ . Comparisons of quantitative variables will be performed by Student's t test for paired data or Wilcoxon test. Concordance between MRI- and traditional test will be determined by the Kappa statistical method as described by Landis and Koch, and  $\kappa$  will be interpreted as follows:  $\kappa$  value of 0 indicates poor agreement;  $\kappa$  value of 0.01–0.20, slight agreement;  $\kappa$  value of 0.21–0.40, fair agreement;  $\kappa$  value of 0.41–0.60, moderate agreement;  $\kappa$  value of 0.61–0.80, substantial agreement; and  $\kappa$  value of 0.81–1; almost perfect. p-value less than 0.05 will be considered statistically significant, and all p-values will be based upon two tailed tests. Statistical analysis will be performed using SPSS for Windows (SPSS Inc, Chicago, Illinois USA).

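### The primary kappa has no fixed reference: under several readings the protocol permits, a stress cMRI that copies the errors of echo scores above an error-free one

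*Protocol*

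**What the plan says.** The Primary Endpoint (Protocol section 2) is "Agreement of results between stress cMRI and the current practice constituted by Exercise test, Stress Cardiac Ultrasound and Invasive Angiography". The Primary Objective in the same section names only two of these tests: "To verify the concordance between stress cMRI and conventional technique (angiography, eco-stress". Neither place says how the tests combine into one result, or which prevails when they differ.

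Section 1 (Background) gives angiography a special status: "coronary angiography (CA) is considered the gold standard for detection of coronary lesions necessitating possible interventions". The endpoint does not carry this over.

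Section 4.4 fixes the statistic: "Concordance between MRI- and traditional test will be determined by the Kappa statistical method". It then attaches absolute labels, for example "value of 0.41–0.60, moderate agreement" and "value of 0.81–1; almost perfect". No comparison of the conventional tests with each other is mentioned, although section 4.3 schedules all of them for every child and its Other Exams part puts them on the same day.

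**The concern.** Kappa treats the two ratings symmetrically. If the comparator is wrong in some children, a cMRI that is right in those children loses agreement, and a cMRI that makes the same mistake gains it. The maximum that an error-free cMRI can reach is then set by the comparator's errors and by prevalence, while the bands in section 4.4 are read as if 1 were always attainable.

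The Background says that, if the results support it, stress cMRI is to replace the whole conventional work-up, angiography included. A primary result that can place a worse cMRI above a better one is a poor basis for that step. Without a benchmark, a label such as moderate also does not show whether cMRI or the comparator is at fault.

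**Working it through.** The protocol states no target kappa and no derivation of the 15 patients, so there is no figure of its own to reproduce.

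**Inputs.** Test accuracies are assumptions, because the protocol gives none: echo sensitivity/specificity 0.80/0.85, exercise test 0.60/0.75, angiography error-free, errors independent given true status. Prevalence in the enrolled mix is not given either. I use 7.5% (the middle of the Background's 7–8%, which refers to symptom-free children after arterial switch), 20%, 30% and 50%.

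**Formula.** κ = (Po − Pe)/(1 − Pe), with Po the observed and Pe the chance agreement in the expected 2×2 table.

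**Worked cases at 20% prevalence.** Echo is positive in 0.2×0.80 + 0.8×0.15 = 0.28 of children.

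- *Echo alone, error-free cMRI.* Po = 0.16 + 0.68 = 0.84. Pe = 0.2×0.28 + 0.8×0.72 = 0.632. κ = 0.208/0.368 = 0.57. A copy of echo scores 1.00 by construction.
- *Echo or angiography positive.* The reference is positive in 0.2 + 0.8×0.15 = 0.32. Error-free cMRI: Po = 0.88, Pe = 0.2×0.32 + 0.8×0.68 = 0.608, κ = 0.272/0.392 = 0.69. Echo copy: it differs only where echo misses disease (0.04), so Po = 0.96, Pe = 0.28×0.32 + 0.72×0.68 = 0.5792, κ = 0.3808/0.4208 = 0.90.
- *Any of three positive.* Composite specificity is 0.85×0.75 = 0.6375, so the reference is positive in 0.2 + 0.8×0.3625 = 0.49. Error-free cMRI: Po = 0.71, Pe = 0.506, κ = 0.204/0.494 = 0.41. Echo copy: disagreement is 0.04 + 0.8×0.85×0.25 = 0.21, Po = 0.79, Pe = 0.5044, κ = 0.2856/0.4956 = 0.58.
- *Majority of three.* Sensitivity is 1 − 0.2×0.4 = 0.92 and specificity 1 − 0.15×0.25 = 0.9625, so the reference is positive in 0.184 + 0.03 = 0.214. Error-free cMRI: Po = 0.954, Pe = 0.6716, κ = 0.2824/0.3284 = 0.86. Echo copy: disagreement is 0.2×0.2×0.6 + 0.8×0.15×0.75 = 0.114, Po = 0.886, Pe = 0.62584, κ = 0.26016/0.37416 = 0.70.

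**All prevalences (error-free cMRI / echo copy).**

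| Reference | 7.5% | 20% | 30% | 50% |
|---|---|---|---|---|
| Echo alone | 0.37 / 1.00 | 0.57 / 1.00 | 0.62 / 1.00 | 0.65 / 1.00 |
| Echo or angiography | 0.46 / 0.95 | 0.69 / 0.90 | 0.77 / 0.87 | 0.85 / 0.80 |
| Any of three | 0.21 / 0.53 | 0.41 / 0.58 | 0.51 / 0.60 | 0.64 / 0.59 |
| Majority | 0.75 / 0.57 | 0.86 / 0.70 | 0.88 / 0.74 | 0.88 / 0.77 |
| Angiography alone | 1.00 / 0.37 | 1.00 / 0.57 | 1.00 / 0.62 | 1.00 / 0.65 |

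**Sensitivity to the assumptions.** With echo 0.90/0.90 and exercise test 0.70/0.80, the 20% figures are 0.72 / 1.00 (echo alone), 0.78 / 0.95 (echo or angiography), 0.51 / 0.65 (any of three), 0.93 / 0.78 (majority) and 1.00 / 0.72 (angiography alone). With angiography at 0.95/0.95 and the other tests as in the table, they are 0.57 / 1.00, 0.62 / 0.83, 0.38 / 0.54, 0.81 / 0.68 and 0.85 / 0.49. The direction at 20% is the same in all three settings.

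**In 15 children.** Take 3 true positives, an error-free cMRI and a reference with 3 false positives. Po = 12/15 = 0.80, Pe = 0.2×0.4 + 0.8×0.6 = 0.56, κ = 0.24/0.44 = 0.55, labelled moderate. Sampling error comes on top: at 30% prevalence and a 0.80/0.85 reference, 20,000 simulated tables of 15 gave a 95% range for κ of about 0.07 to 1.00.

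**The case against.** The strongest reply is that angiography is already among the comparators. Section 4.4 speaks of the traditional test in the singular, so a separate kappa for each test, including cMRI versus angiography, is a fair reading. That stands as a possible reading. Even then, nothing ranks the cMRI–angiography kappa above the cMRI–echo kappa, so the primary result stays open.

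A reader might infer that an error-free cMRI can reach only fair or moderate while an echo copy is almost perfect. The protocol does not support this in general. Under the table's assumptions that full contrast appears only for echo alone up to about 20% prevalence and for echo-or-angiography near 7.5%. For the three-test endpoint with any test positive, the copy is only moderate. Under a majority or angiography-decisive rule the order is correct, and at 50% prevalence the two any-positive composites no longer favour the copy.

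A reader might also infer that the trial seeks a more accurate test. The Background argues for a safer, radiation-free and cheaper substitute, and for that purpose agreement with current practice is a coherent pilot target. The bands are descriptive, with no success threshold tied to them. Both points soften the consequence but do not fix the comparator.

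Finally, angiography assesses anatomy and pressures, while stress echo assesses wall motion and thickening by segment. Judging everything against angiography would penalise functional findings that it does not measure. This stands and limits the fix to coronary lesions.

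Deferral to an unseen analysis plan does not answer the point, because the protocol itself states the comparator, the statistic and the reading scale.

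**Conclusion.** The concern holds in a conditional form. The protocol names two different sets of comparators, gives no hierarchy or combination rule, and reads kappa on absolute bands, although it names a gold standard for coronary lesions. Under three permitted readings (echo alone, echo or angiography, any of three), an echo copy scores above an error-free cMRI at prevalences of 7.5% to 30%, by 0.09 (0.60 − 0.51) to 0.63 (1.00 − 0.37) in the table. Against angiography alone, or by majority, the order is right at every prevalence tried.

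The sizes rest on assumed accuracies, independent errors and an unknown prevalence; the 7.5% case may not describe a group that includes children with previously diagnosed disease. The ceiling itself does not depend on those particular values: it follows from any error in the comparator. This should be changed, but it does not invalidate the pilot.

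**What to change.** In the Primary Objective, the Primary Endpoint and section 4.4:

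1. Name cMRI versus angiography as the primary agreement analysis, for coronary lesions only.
2. Report stress echo versus angiography and exercise test versus angiography beside it, in the same children and with confidence intervals, as the benchmark for reading the cMRI result.
3. Report cMRI versus stress echo separately, for wall motion, where angiography is not the reference, and do not interpret it by the band labels alone.
4. Use the same list of comparators in the objective and the endpoint.

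The cost is wording and slightly more analysis, since all the tests are already scheduled. With 15 children the benchmark comparison will be descriptive and imprecise, and the text should say so.

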**Secondary Endpoints:**

- Efficacy of stress cMRI: Predictive value of stress cMRI to determine the incidence of post-surgical complication of switch repair, and other pathological conditions affecting coronary arteries in natural history
- Safety: to investigate Advers Events (AE) to Contrast Medium and pharmacological stress agent

### 3. STUDY DESIGN:

Mono-centre, pilot, prospective interventional study.

cMRI exam with injection of Contrast Medium is considered a safe and robust technique to study congenital heart disease in pediatric patient. At Gaslini Institute, our Cardio-Radiology team accounts for more than 1000 cMRI exams of congenital heart disease performed in pediatric patients, without major adverse events reported.

Furthermore, in our centre, Dobutamine is routinely administered to all patients during diagnostic stress procedures (Stress Cardiac Ultrasound and Invasive Angiography), which correspond to the current practice to investigate coronary arteries anomalies according to international guidelines.

Therefore, stress cMRI with Dobutamine stress agent (stress cMRI), from a procedural perspective, represent the combination of two orders of exams routinely performed (cMRI and stress diagnostic series of exams) without additional risk for the patient, but with the advantage of non-invasiveness and lack of radiation, less laborious for the Patient and less expensive for the Healthcare.

### 4. STUDY PROCEDURES

The study population will be recruited, over a period of approximately 24 months, from children attending the ward and the outpatient clinics of the cardiologic paediatric unit, in accordance with the following inclusion criteria.

4.1 Inclusion Criteria are: Between 8 and 18 years-old patients symptomatic and non, with suspected or previously diagnosed coronary arteries disease: Coronary artery re-implantation after arterial switch, ALCAPA Syndrome, other anomalies of origin or pathway, replacement of aortic valve with pulmonary autograft (Ross procedure), Kawasaki disease, primary dilatative cardiomyopathy, coronary atresia, familial Hypercholesterolemia, bicuspid aortic valve, chest pain, exertional dyspnea of suspected coronary artery nature, coronary artery fistula.

4.2 Exclusion criteria are: General contraindication to MRI (non MRI compatible device: vascular clips, foreign bodies, coronary and peripheral artery stents, aortic stent grafts, prosthetic heart valves and annuloplasty rings, cardiac occluder devices, vena cava filters and embolisation coils, haemodynamic monitoring and temporary pacing devices, haemodynamic support devices, permanent cardiac pacemakers and implantable cardioverter-defibrillators, retained transvenous pacemaker and defibrillator leads, cochlear implants, claustrophobia, pregnancy and postpartum), contraindication to contrast agent (renal insufficiency, hypersensitivity to the Dotarem active substance or to any of the excipients:), contraindication to stress agent (hypersensitivity to Dobutamine active substance or to any of the excipients; severe arterial hypertension ( $\geq 220/120$  mmHg), unstable angina pectoris, significant aortic stenosis, complex cardiac arrhythmias including uncontrolled atrial fibrillation, hypertrophic obstructive cardiomyopathy, myocarditis, endocarditis, pericarditis, uncontrolled congestive heart failure, previous manifestations of hypersensitivity to dobutamine, refuse to join the protocol and relative off-label procedures.

A total number of 15 patients fitting the above criteria is the target of our study.

### 4.3 Study Procedure

#### METHOD

- 1) Ask for permission of local ethic board
- 2) Identify all patients in follow-up at Gaslini Institute, with suspected or previously diagnosed coronary arteries disease
- 3) Patients selection based on inclusion criteria
- 4) Patient call and first clinical visit, which includes explanation of research protocol and consent form signature
- 5) Stress CardiacMRI scan, ECG and Stress Cardiac Ultrasound exam, Exercise Test, Coronary Angiography.

### EXAM PREPARATION

Patients were asked to abstain from caffeine intake and to refrain from taking anti-anginal medications including beta-blockers 24 h prior to the exam. Theophylline must not be used for at least 12 hours before exam. Dipyridamole must not be used for at least two days before exam

Doctor have to explain to patient and parent the tasks of the exam, the benefits and the risks related to the subadministration of medications, including the Dobutamine. In particular, parents have to sign the consent form for off-label use of Dobutamine, consent form for Contrast Medium injection (Dotarem, Guerbet ITALY), and metal check list for in order to exclude patients with contraindications to MRI.

Nurse staff, under the supervision of a Doctor, should provide peripheral venous cannulation, thoracic four-lead VCG signal placement for MRI cardiac synchronization and thoracic twelve-lead electrodes for cardiac activity monitor.

Total Dotarem dose to inject during exam is calculated by the formula 0,1 mmol/kg.

Baseline HR and BP were obtained at rest prior to stress exam in the supine position. Peak HR was defined as the highest HR during the stress perfusion scan. Peak BP was defined as the BP corresponding to HR peak. Heart rate response (HRR) and blood pressure response (BPR) were calculated ( $\text{HR response} = [(\text{HR}_{\text{peak}} - \text{HR}_{\text{baseline}})/\text{HR}_{\text{baseline}}] \times 100$ ;  $\text{BP response} = [(\text{BP}_{\text{peak}} - \text{BP}_{\text{baseline}})/\text{BP}_{\text{baseline}}] \times 100$ ).

Proper hospital clothes and bladder emptying before entering MRI scanner room are recommended.

A 12-lead ECG was performed before and after the exam. Owing to magnetohydrodynamic effects causing ECG signal distortion, ECG tracing during examination was used only for gating purposes. Oxygen saturation, blood pressure (BP), and HR were monitored throughout the exam.

### Cardiac MRI PROTOCOL

MRI scanner: Philips Achieva 1.5 T. 32 Channel Cardiac Coil.

A. Scout sequences

B. SSFP 2-Chamber left, SSFP 2-Chamber right, SSFP 4-Chamber

C. DOBUTAMINE in increments of 10  $\mu\text{g}/\text{kg}$  body weight/minute every 3 minutes starting at 10  $\mu\text{g}/\text{kg}$  body weight/minute until target heart rate [ $85\% \times (220 - \text{age})$ ] reached.

- D. Dotarem injection (0,1 mmol/kg, 2 ml/sec) when the target heart rate is reached
- E. Stress perfusion Images in Short Axis and 4-Chamber
- F. Cine Short Axis from base to apex for volumetric analysis
- G. Late Gadolinium enhancement
- H. Rest perfusion Images in Short Axis and 4-Chamber
- I. 3D Navigated SSFP in transversal plane
- L. Aorta and Pulmonary flow

Patients were queried about their symptoms before and after Dobutamine administration. Sublingual nitroglycerine and iv metoprolol are available for severe and persistent chest pain during or after the exam.

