#### STAFF, MEDICAL AND TECHNICAL EQUIPMENT

Hospital staff involved in stress cMRI exam is composed by: Radiologist, Cardiologist, Radiographer, Nurse. In case of necessity, first aid is guaranteed by Radiologist and Cardiologist in site, but in-Hospital Anesthetist Resuscitator is 24 hours 365 day ready to intervene for emergency related to MRI exams.

Emergency medical supplies, in recovery room: metoprololo, esmololo, nitroglycerine, adrenaline, betametasona

Medical device MRI compatibile, in scanner room: Contrast Medium pump, Dobutamine pump, cables and electrodes for four-lead VCG signal, cables and electrodes for cardiac monitoring, sat O2, heart rate and arterial blood pressure devices

Medical device not MRI compatibile, in control room: Contrast and Dobutamine pump command module, vital parameter monitor (12 lead ECG trace, blood pressure, heart rate, sat O2).

Medical device not MRI compatibile, in recovery room: vital parameter monitor (12 lead ECG trace, blood pressure, heart rate, sat O2), defibrillator

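### Off-label dobutamine is escalated with the target heart rate as its only stated exit: there is no maximum rate, no stopping event, and no instruction for a child who misses the target

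*Protocol*

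**What the plan says.** Section 4.3 of the Protocol, under Cardiac MRI PROTOCOL, sets the stress procedure. Step C begins dobutamine at 10 µg/kg/min and raises it by the same amount every 3 minutes, "body weight/minute until target heart rate", defined as 85% × (220 − age). Step D is "Dotarem injection (0,1 mmol/kg, 2 ml/sec) when the target heart rate is reached", and step E, stress perfusion imaging, follows. Parents sign a "consent form for off-label use of Dobutamine" (EXAM PREPARATION).

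The text nearest to a safety rule is in five places:

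- **Rescue drugs:** "Sublingual nitroglycerine and iv metoprolol are available for severe and persistent chest pain during or after the exam".
- **Monitoring:** oxygen saturation, blood pressure and heart rate are followed throughout the exam (EXAM PREPARATION).
- **Staff and equipment:** a cardiologist and a radiologist attend. The control room holds the "Contrast and Dobutamine pump command module, vital parameter monitor (12 lead ECG trace, blood pressure, heart rate" and saturation display.
- **Exclusions (4.2):** these include unstable angina, complex arrhythmias, significant aortic stenosis and blood pressure of at least 220/120 mmHg.
- **Local experience (section 3):** dobutamine is already used routinely in the centre's stress procedures.

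On the ECG, EXAM PREPARATION says that because of signal distortion "ECG tracing during examination was used only for gating purposes". The same subsection also calls for "thoracic twelve-lead electrodes for cardiac activity monitor", and the equipment list includes a 12-lead trace in the control room.

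**The concern.** A titration rule with an efficacy target but no safety limit is incomplete for exactly the child who does not respond as expected. That child continues to be escalated unless someone decides otherwise, and the protocol does not say at what rate or on which event they must. The Protocol's own ADVERSE EVENTS text names cardiac arrest, ventricular arrhythmia and infarction from induced ischaemia, as well as AV block, hypotension and bronchoconstriction. It provides for recording such events, but ties none of them to ending step C.

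There is also a consequence for the data. Contrast depends on reaching the target, so a child stopped early has no stated route to stress perfusion. The protocol states that "Peak HR was defined as the highest HR during the stress perfusion scan". Without that scan, peak heart rate, peak blood pressure (taken at peak heart rate) and both response percentages are undefined. A child stopped because of ischaemia may well be one with true disease, so such losses need not be random with respect to the primary agreement endpoint.

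Dose limits and stopping events are study procedures. An analysis plan would not normally supply them.

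**Working it through.** The protocol states no figure to reproduce here. The check is a search of the whole text, plus arithmetic on step C.

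**Inputs.** Start and increment 10 µg/kg/min, interval 3 minutes, target 0.85 × (220 − age) (step C); ages 8 to 18 (4.1); 15 patients (4.2).

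**Target heart rate**

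- Age 8: 0.85 × 212 = 180.2 bpm
- Age 12: 0.85 × 208 = 176.8 bpm
- Age 18: 0.85 × 202 = 171.7 bpm

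**Escalation as written.** In step k the rate is 10k µg/kg/min, from minute 3(k − 1) to minute 3k. The cumulative dose after k steps is 3 × 10 × (1 + … + k) = 15k(k + 1) µg/kg.

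| k | Minutes | Rate (µg/kg/min) | Cumulative (µg/kg) |
|---|---|---|---|
| 1 | 0–3 | 10 | 30 |
| 2 | 3–6 | 20 | 90 |
| 3 | 6–9 | 30 | 180 |
| 4 | 9–12 | 40 | 300 |
| 5 | 12–15 | 50 | 450 |
| 6 | 15–18 | 60 | 630 |
| 8 | 21–24 | 80 | 1080 |

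No largest k is stated. The table shows what the rule permits and does not predict exposure.

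**Does anything else in the text bound the infusion?**

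- The exclusions, including the 220/120 mmHg figure, apply before entry and not during infusion.
- Monitoring carries no threshold and no action.
- Rescue drugs are available, but the text does not tie their use to stopping dobutamine.
- Symptoms are asked about before and after dobutamine, with no action attached.
- Staff can stop the pump, but no trigger is given.
- Section 3 cites routine use without a dose, and the stress ultrasound description under OTHER EXAMS gives no dose or stopping rule that could apply by reference.

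**Missed targets.** The protocol gives no rate. Two illustrations, both resting on assumptions:

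- If 1 to 3 of the 15 children miss: 1/15 = 6.7% to 3/15 = 20% of exams.
- If each child misses independently with probability p, the chance of at least one miss is 1 − (1 − p)^15. This is 54%, 79%, 96% and 99.5% for p = 5%, 10%, 20% and 30%; the expected numbers are 0.75, 1.5, 3.0 and 4.5 children.

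**The case against.** The strongest reply is that the literal reading is a worst case. Escalation ends in every child who reaches the target, and beta-blockers are withheld for 24 hours, which makes a miss less likely. A cardiologist is present with the pump under control and vital signs on display. Having metoprolol on hand for chest pain during the exam implies that dobutamine would stop at that point. The centre uses the drug routinely and says its practice follows international guidelines, so a local ceiling may well exist. The attachments, including the consent material, are not available to check. Heart rate and blood pressure responses are not endpoints. The ECG point is partly separate, since a distorted trace can be rejected for diagnosis and still be displayed.

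Much of this stands as mitigation. It is fair to say only that the protocol does not write down or cite a limit, not that local practice lacks one. The implied stop covers one symptom and is not an instruction. The unseen attachments cannot be ruled out, but section 4.3 does not refer to them for dosing. The percentages are assumed, and nothing rests on them. The ECG conflict remains relevant because an arrhythmia or AV-block stopping criterion needs a usable signal.

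One further caution is sound: parts of the adverse event text, such as arterial vasodilation, read as generic to pharmacological stress agents, so that list should not be copied unexamined into stopping criteria for dobutamine.

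**Conclusion.** The concern holds and must be fixed. In the text available, step C has one stated exit (180.2 bpm at age 8, falling to 171.7 bpm at age 18), no maximum rate, no terminating event and no instruction for a missed target, and step D inherits the gap. The hazard is one the protocol itself names, in children with suspected or known coronary disease receiving an off-label drug.

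The effect on the data is real, but its size is unknown. Each missed target is 1 of 15 exams (6.7%), and how many occur cannot be derived from the protocol. The conclusion rests on the wording of steps C and D and on the absence of any limit elsewhere in the visible text. It does not depend on an assumed miss rate.

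**What to change.** Amend section 4.3 as follows:

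1. **Step C, ceiling.** State a maximum dobutamine rate, with the value set by the clinical team.
2. **Step C, stopping events.** End the infusion, whether or not the target has been reached, on severe chest pain or other evidence of ischaemia, significant arrhythmia or AV block, a blood pressure change beyond a stated limit, or bronchospasm. The clinical team should confirm that the list suits dobutamine.
3. **Step D, below target.** Say whether contrast and stress imaging go ahead at the maximum rate when the target has not been reached.
4. **ECG.** Reconcile EXAM PREPARATION with the equipment list in one sentence: state whether the in-scanner trace is used for monitoring, and name the signal on which the rhythm criteria rest.

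The cost is a short protocol amendment. Some exams will end below the target heart rate and must be reported as such.
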